10. STUDY ENDPOINTS*

The main dependent variable is patient tobacco cessation rate (quit rate) at six months. The primary independent variable is assignment to intervention or comparison group. We have designed a patient-level analysis around point prevalence cessation. We will use a two-sided chi-square test for equality of proportions to test whether the quit rates differ between the groups. If we need to adjust for any covariates, we will include them in a multivariable logistic regression model with smoking cessation as the outcome and group status as the main independent variable. Our secondary outcome measure is self-efficacy. We hypothesize that the self-efficacy (SEQ-12) scores will be higher in intervention than comparison. The SEQ-12 is a 12-item questionnaire with 6 questions under two domains, internal and external stimuli. Two composite scores are

INVESTIGATOR STUDY PLAN - REQUIRED

computed for each of these domains by adding the individual items. These data will be collected at baseline and at the follow-up. The aim is to assess the effect of intervention over the immediate period, i.e., do the scores improve more from baseline to six months for the intervention group than the control group. We will compute the scores at baseline six months in the two groups.

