Randomization: Participants will be blinded to randomization. All smokers will be told that they will be randomized to one of two different ways to support thinking about quitting smoking. In addition to our primary points of innovation, we will use an innovative mHealth randomization strategy. Allocation of participants to study arms will be based on a permuted block scheme in which treatment assignments are made within blocks so that numbers assigned to each treatment arm are equal after a block has been filled. Blocks of various sizes (2, 4, 6) will be used in random order to facilitate allocation concealment. Similar to our prior technology-based trials, we will embed randomization within the technology. At enrollment, study staff will conduct a baseline survey with participants. At the end of the baseline assessment survey, study staff will enter the participant ID and participant mobile phone number from the survey into our texting system, and the system will look up the next allocation within the table, and adapt based on the allocation assignment. Using this technique, both smokers and the study staff will be blinded to allocation during the initial session. In our prior technology-assisted randomized trials, we have embedded randomization within the technology.

INVESTIGATOR STUDY PLAN - REQUIRED

Baseline data collection (see M2Q2_Baseline_Survey): will include patient demographics, comorbidities, cessation treatment beliefs scale, and self-efficacy. Self-efficacy will be measured with the SEQ-12.^[36] The SEQ-12 is a 12-item questionnaire with 6 questions pertaining to internal stimuli and external stimuli domains each. Two composite scores are computed for each of these domains by adding the individual items. Self-efficacy will be assessed at baseline and follow-up.

Measures through texting: as described above, we will have data collected through texting, including measure of readiness to quit, abstinence assessments, and interest in use of the quitline.

Quitline referral tracking – quitline staff will record details of intake assessment (time on call, readiness to quit, quit date and goal-setting) and fidelity of follow-up call completion. They will also document distribution of NRT lozenge and smoker use of NRT during follow-up.

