To preserve the power of randomization, all primary analyses will be on an intent-to-treat basis. However, secondary analyses will explore dose-response effects among those with variable levels of adherence to the intervention. All analyses will be two-sided and alpha error will be set at 0.05. We will begin the statistical analysis by examining univariate statistics (means, medians, standard deviations and 95% confidence intervals) and distributions. We will examine the balance of participant characteristics by study groups and account for any imbalances in our multivariable analysis. As appropriate, group differences will be tested using chi-square tests of independence (categorical variables), Z-test or t-test (continuous variables) or the equivalent non-parametric tests depending on the distribution of the variables. In accordance with best practice, differences in baseline characteristics of the intervention and comparison groups will be established based on standardized differences, rather than on tests of statistical significance.^[39, 40]

Main outcome: six-month point prevalence cessation: The main dependent variable is patient tobacco cessation rate (quit rate). The primary independent variable is assignment to intervention or control group. We have designed a patient-level

INVESTIGATOR STUDY PLAN - REQUIRED

analysis around point prevalence cessation. We will use a two-sided chi-square test for equality of proportions to test whether the quit rates differ between the groups. If we need to adjust for any covariates, we will include them in a multivariable logistic regression model with smoking cessation as the outcome and group status as the main independent variable.

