Dealing with missing outcomes data: We will make every effort to maximize participant retention in the study. For our short-term evaluation, we do not expect high rates of attrition; however, we approximate that there will be about 15-20% attrition based on previous studies. Thus, although we plan to randomize 750, our power calculations for outcomes are based on 600 completing follow-up. We will monitor recruitment and retention, and inflate our sample as needed to achieve the resulting sample of 600 completing 6-months. We will estimate potential bias due to drop-outs in our study and perform a series of sensitivity analyses to understand the extent of this bias. We will assess the extent of missing data by treatment group for each time point. A challenge for all cessation induction trials is missing outcome data.^[43-45] This is especially true in light-touch technology-assisted interventions. Most often, a complete case or missing case (penalized imputation) indicative of smoking analysis has been implemented in logistic regression. However, the reason that we did not use penalized imputation as the primary outcome is that new literature has been published suggesting that penalized imputation (or missing=smoking) is not a conservative approach, and can be biased toward the intervention.^[44] Thus, for studies with missing cessation data greater than 10-20%, experts recommend using selection models to examine the robustness of findings.^[43] We will compare characteristics of patients who remained in the trial and those lost to follow-up. Using a generalized linear model with a logit link to evaluate cessation outcomes and GEE methods to account for clustering within practices, we will

INVESTIGATOR STUDY PLAN - REQUIRED

implement a selection model using inverse probability weighting to determine the potential effect of missing data. First, based on covariates available within the dataset, we will develop a logistic regression model to predict the amount of missing data. Then, we'll calculate the inverse probability of not being missing and weight the main analysis by this probability.^[46]

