Secondary Outcome: Self-efficacy: We hypothesize that the self-efficacy (SEQ-12) scores will be higher in intervention than comparison. The SEQ-12 is a 12-item questionnaire with 6 questions under two domains, internal and external stimuli. Two composite scores are computed for each of these domains by adding the individual items. These data will be collected at baseline and at the follow-up. The aim is to assess the effect of intervention over the immediate period, i.e., do the scores improve from baseline to six months for the intervention group than the control group. We will compute the scores at baseline six months in the two groups. We will evaluate whether the intervention differences change over time (i.e., is there an intervention and time interaction?). To address this question, we will use a random-effects model of the form:

$$y_{ijt} = \alpha + \gamma_i + \beta_j + \delta_t + (\beta\delta)_{it} + u_{ij} + e_{ijt}$$

where, y_{ijt} is response at time t for the j -th subject in the i -th group, α is the intercept, γ_i is the vector of effects associated with covariates, β_j is the main effect for the intervention group, δ_t is the main effect for time, $(\beta\delta)_{it}$ is the effect for the interaction between intervention group and time, u_{ij} is the random effect corresponding to the j -th subject in the i -th group (assumed to be $N(0, \sigma_u^2)$), and e_{ijt} is the term accounting for sampling variability (assumed to be $N(0, \sigma_e^2)$). The coefficient $(\beta\delta)_{it}$ is the estimate of the interaction term which, if significant, indicates that the intervention effect varies significantly with time. We will first generate the variance-covariance matrix to determine the appropriate covariance structure.

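### The self-efficacy (SEQ-12) analysis tests group-by-time with the pre-randomisation score as an outcome, in effect a difference in change scores: valid, but usually less precise than adjusting for baseline

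*Combined protocol and SAP*

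**What the plan says.** Section 10 (Study Endpoints) names self-efficacy as the secondary outcome, with two SEQ-12 composites (internal and external stimuli), and asks "do the scores improve more from baseline to six months for the intervention group than the control group". Section 11 (Procedures Involved) fixes the timing: "Self-efficacy will be assessed at baseline and follow-up", with a single follow-up at six months. Under Randomization in the same section, allocation comes after the baseline survey: "At the end of the baseline assessment survey, study staff will enter the participant ID", and only then does the system look up the next assignment. Allocation is 1:1 in permuted blocks.

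Section 13 (Secondary Outcome: Self-efficacy) states the test, "We will evaluate whether the intervention differences change over time (i.e., is there an intervention and time interaction", and the tool, "we will use a random-effects model of the form" that follows in the text. The response is indexed by time. The model has a group main effect, a time effect, their interaction, a subject random effect and a vector of unnamed covariates. On covariance it says only: "We will first generate the variance-covariance matrix to determine the appropriate covariance structure".

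Elsewhere in section 13, the general analysis text promises to "account for any imbalances in our multivariable analysis". On numbers it says "although we plan to randomize 750, our power calculations for outcomes are based on 600 completing follow-up".

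**The concern.** The baseline survey is finished before allocation, so any difference between arms in true mean baseline score is zero by design. The planned model does not use this. Its group main effect lets each arm have its own baseline mean, and the interaction then subtracts the observed baseline difference in full. Subtracting in full is optimal only when the slope of follow-up on baseline is 1. Otherwise it adds noise that a fitted slope would remove.

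Nothing else in the plan supplies baseline adjustment. The general text adjusts only for imbalances that happen to be observed. Baseline SEQ-12 is not named among the covariates, and with complete pairs a time-invariant covariate in this model leaves the interaction unchanged.

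What is at stake is precision, not bias. Section 5 (M2Q2 Theoretical Constructs) calls self-efficacy an important process by which the intervention is meant to raise cessation, and no power is stated for it. The planned test would usually use less of the information already collected than it could.

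**Working it through.** **The plan's own figures.** The only stated power is 91% for cessation (10% v 20%, 300 per arm, two-sided 0.05). The continuity-corrected calculation gives 91.5%; without the correction it is 93.1%. The 750 randomised follows from 600/(1 − 0.20). There is no SEQ-12 figure to reproduce.

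**Inputs from the documents.** Two measurement times, baseline before allocation, 1:1 allocation; 750 baselines and 600 follow-ups, so 375 and 300 per arm.

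**Assumed inputs.** Baseline SD 1, follow-up SD *k*, correlation ρ, equal completers per arm, follow-up missing completely at random.

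**Step 1: what the interaction estimates.** In one simulated data set of 600 complete pairs, the mixed-model interaction was 0.1591 (SE 0.0854) and the difference in mean change was 0.1591 (SE 0.0854). Adding a time-invariant covariate changed neither.

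**Step 2: validity.** Over 8,000 simulated null trials per setting, the interaction rejected in 4.5% to 5.1%. With a true effect of 0.2 SD, it and baseline-adjusted analysis (ANCOVA) both averaged 0.200.

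**Step 3: precision.** Variances by generalised least squares, in units of 2/300, with 0.8 = 300/375:

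- planned = k²(1 − ρ²) + 0.8(1 − kρ)²
- ANCOVA = k²(1 − ρ²)

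The extra term cannot be negative and is zero only when kρ = 1. For example, at k = 1, ρ = 0.3: ANCOVA = 1 − 0.09 = 0.910; planned = 0.910 + 0.8 × 0.49 = 1.302; loss = 0.392/1.302 = 30.1% of the planned variance.

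| k | ρ | Planned | ANCOVA | Loss |
|---|---|---|---|---|
| 1 | 0.3 | 1.302 | 0.910 | 30% |
| 1 | 0.5 | 0.950 | 0.750 | 21% |
| 1 | 0.7 | 0.582 | 0.510 | 12% |
| 1 | 0.8 | 0.392 | 0.360 | 8% |
| 1 | 0.9 | 0.198 | 0.190 | 4% |
| 0.8 | 0.3 | 1.0445 | 0.5824 | 44% |
| 0.8 | 0.5 | 0.768 | 0.480 | 38% |
| 0.8 | 0.7 | 0.4813 | 0.3264 | 32% |
| 1.25 | 0.3 | 1.7344 | 1.4219 | 18% |
| 1.25 | 0.5 | 1.2844 | 1.1719 | 9% |
| 1.25 | 0.7 | 0.8094 | 0.7969 | 2% |
| 1.25 | 0.8 | 0.5625 | 0.5625 | 0% |

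In the k = 1 rows, adjustment makes the standard error 16%, 11%, 6%, 4% and 2% smaller. At 15% attrition (319 pairs and 56 baseline-only per arm) the k = 1 losses are 31%, 22%, 13%, 9% and 4%.

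**Step 4: simulation check (20,000 runs, k = 1).** The SD of the estimate, planned v ANCOVA, was 0.0931 v 0.0778 at ρ = 0.3, 0.0801 v 0.0708 at 0.5 and 0.0623 v 0.0584 at 0.7. The closed form at ρ = 0.3 gives √(1.302 × 2/300) = 0.0932 and √(0.910 × 2/300) = 0.0779.

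**Step 5: illustrative power.** For an assumed 0.2 SD effect, power = Φ(0.2/SE − 1.96). With k = 1 and ρ = 0.3/0.5/0.7/0.8, the planned test has 57.4%/71.0%/89.5%/97.5% and the adjusted one 72.8%/80.7%/92.9%/98.3%.

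**The case against.** The strongest reply is that nothing here is an error. The contrast is valid and answers the question section 10 asks, and preferring a more efficient estimator could be called taste. The size of the gain also rests on assumed values: it is nil at one plausible combination, and with equal SDs the standard error shrinks only 2% to 6% at correlations of 0.7 to 0.9. All of that stands. It limits the grade of the point but does not answer it, since the change costs almost nothing.

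The word never also needs its condition. Common-slope ANCOVA can lose slightly if completers are unequal and slopes differ by arm. With 270 v 330 complete pairs, slopes 1.2 v 0.8 and residual variance 0.3, its variance is 0.002298 against 0.002290 for change scores, a reversal of 0.000008/0.002290 = 0.35%. This is correct arithmetic, but it needs slopes on either side of 1 and unequal completers, and the effect is trivial.

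The third argument is robustness. The planned model keeps participants lost to follow-up and tolerates a wrong covariance well. A common-baseline model with only a random intercept does not. Under 750/600 and ρ of 0.3 to 0.7, its standard errors are about 10% too small at k = 1.25 (type I error 7.8% to 7.9%) and about 14% too large at k = 0.8 (2.5% to 2.6%), against 5.6% and 4.5% for the plan. At k = 1.25, ρ = 0.7 it is even less precise than the plan (0.837 v 0.817). This is a sound reason to rule out that combination. It does not count against ANCOVA, or against the common-baseline model with an unstructured covariance.

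**Conclusion.** The point holds as an inexpensive improvement that should be made, not as a flaw that invalidates the analysis. With equal completers per arm, the planned interaction is never more precise in large samples than a baseline-adjusted comparison, and it is less precise unless kρ = 1. How much is lost cannot be read from the documents. On the assumed grid it is 4% to 30% of the variance with equal SDs, 32% to 44% if the follow-up SD is 0.8 times baseline (ρ 0.3 to 0.7), and 18% down to zero if it is 1.25 times (ρ 0.3 to 0.8). These figures assume follow-up missing completely at random. The 91% power claim concerns cessation only and is untouched.

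**What to change.** In section 13, for each SEQ-12 composite, name as the main analysis the six-month difference between arms adjusted for baseline score (ANCOVA).

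If every randomised participant with a baseline score is to stay in the model, use instead a repeated-measures model with one common baseline mean: no group main effect, a time term and a group-by-six-months term. State an unstructured covariance or robust standard errors. With an unstructured covariance its variance equals that of ANCOVA in this design. Do not pair the common baseline with a random intercept alone. Section 13 leaves the covariance structure open, so it can be named now. While editing, correct the printed formula, which indexes the group effect by the letter defined as the subject.

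The cost is analysis wording only, since baseline SEQ-12 is already collected. ANCOVA leaves out those without a six-month score, about 150 of 750 at 20% attrition. The common-baseline model keeps them but depends more on the covariance than the planned model does.

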14. PROVISIONS TO MONITOR THE DATA TO ENSURE THE SAFETY OF SUBJECTS*

Consistent with NIH policy, the purpose of the Data and Safety Monitoring Plan (DSMP) is to specify the procedures and rationales of the current study to ensure the safety of participants and the validity and integrity of the data. This plan specifies who will examine the data and any adverse events, how often, and what they are authorized to do. Since this trial takes place in Vietnam and is a Phase III study including NRT and our behavioral intervention, we will establish a Data and Safety Monitoring Board (DSMB) at the Institute of Population, Health, and Development (PHAD) in Vietnam and a Data Oversight Committee (DOC) at the University of Massachusetts Medical School.

The DSMB is charged with reviewing protocols and consent documents for this trial, monitoring safety issues throughout the study and the quality of the accumulating data, providing guidance on interim analyses and stopping rules. They will also serve as a liaison among the study investigators, the PHAD IRB, the UMMS DOC, the UMMS Office of Human Research Protections (IRB), and the National Institute of Health (NIH).

DSMB Membership

The DSMB will be comprised of persons with no direct involvement in the study or conflict of interest with the research team conducting the randomized trial. The DSMB will include individuals with expertise in: 1. Clinical research in Tobacco; 2. Health Informatics and/or Information Technology intervention research; and 3. Biostatistical experience.

DSMB Responsibilities and Actions

The DSMB will have the following responsibilities:

- 1.) Review and approve, disapprove, or suggest modifications to the randomized trial protocol and/or consent documents to assure both scientific integrity and that the study adheres to human subject protection policies.
- 2.) Monitor, provide feedback, and report on scientific and ethical issues related to study implementation for the protection of human subjects and advise on ethical issues related to adverse events. The DSMB will monitor adverse event reports for purposes of determining whether their nature, frequency and severity are consistent with expectations. The DSMB, in coordination with the PI, [name], reports to the IRB and NIH any unanticipated problems involving risks to subjects. Along with the IRB and NIH staff, the DSMB can recommend remedies or other appropriate actions such as introducing new monitoring protocols, altering inclusion or exclusion criteria, or recommend changes in the informed consent documents.

INVESTIGATOR STUDY PLAN - REQUIRED

- 3.) Ensure that the study protocol maintains patients' confidentiality in a manner that is appropriately balanced against issues of clinical care and safety.
- 4.) Monitor data regarding the efficacy of the study. The DSMB will review data for outcome events by treatment group. The DSMB will decide whether the trial should continue with or without further enrollment of new participants. The DSMB has the authority to halt the trial as needed.
- 5.) To monitor data management activities. The DSMB may ask to review data relevant to quality control. The DSMB will review requests for interim analyses and approve, disapprove, require additional information, or defer decisions.

DSMB Meeting Schedule

Once patient recruitment for the trial has begun, the DSMB will meet two times per year or more frequently as determined by the DSMB members. The DSMB meetings will be conducted via teleconference. The Board and the PI will decide upon the format of the meetings. Additional telephone conferences will be held if doing so is recommended by the DSMB.

DSMB Reports

The PI, [name], and study team will submit statistical reports to the DSMB one week prior to the scheduled meeting. These reports will include all reported data up to and including 14 days prior to the reporting deadline (except for Serious Adverse Events, which are to be reported within 24 hours of the event). For each meeting at which the study is to be considered or monitored, the investigators will present an overall progress statement. This brief statement should contain the assurance that the investigators have considered the clinical trial's progress and that there is or is not evidence of safety issues that should be addressed by the DSMB. In addition, the report will contain any changes to the study protocol, recruitment, retention, and tracking of study patients (using a CONSORT diagram), a summary of all adverse events and severe adverse events, baseline measures and demographics of all patients reporting adverse events, and any other information requested by the DSMB.

Data Oversight Committee

The Data Oversight Committee (DOC) will be responsible for ensuring the project is in line with US Regulations and Compliance of human subject research. The DOC will be comprised of individuals with no direct involvement in the study or conflict of interest with the research team conducting the randomized trial. The DOC will include individuals with expertise in: 1. Clinical research in Tobacco; 2. Health Informatics and/or Information Technology intervention research; and 3. Biostatistical experience.

The DOC will be responsible for reviewing all minutes, reports, and recommendations of the DSMB meetings and providing appropriate feedback to the PI, [name]. The DOC will convene within 2 weeks following each DSMB meeting with DOC meeting materials, including DSMB meeting minutes, being circulated at least 1 week prior to meeting. The DOC meeting will be conducted via teleconference.

INVESTIGATOR STUDY PLAN - REQUIRED

Adverse Events

[name] will provide monitoring for all adverse events. All adverse events/effects will be recorded in the research record and any reports of adverse events will be reviewed by the PI or his designee, who are available 24 hours/day. All non-serious adverse events will be reviewed in a weekly study meeting. Adverse event documentation will include description of the event, ratings of severity and relationship to study medication/study procedures, and follow-up (if any) and outcome. All adverse events, both serious and non-serious, will be summarized in the required report to the IRB Committee(s) for annual study review and renewal. The PI will then comment on the implications to future participants and the need for changes to the risk: benefit ratio for participating in the trial.

Serious Adverse Events

The PI will report to the IRBs, if mandated to do so, all serious adverse events that occur in the context of this randomized trial. In general, a serious adverse event is defined as a harmful and undesired effect resulting from a medication or other intervention. The event is also: life threatening/results in death OR disabling/incapacitating OR requires or prolongs hospitalization OR was otherwise unanticipated, related to the study procedures or could lead to one of the other serious event conditions

According to UMMS IRB policy, all adverse events and serious adverse events that occur in the proposed study must be reported to the institution's IRB, regardless of whether they are study related or not.

IRB Approval

All study protocols, including the Data Safety and Monitoring Plan, will be submitted and approved by the UMMS and PHAD IRBs.

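### The SAE definition in Section 14 requires attribution to a treatment, so an unattributed death or hospitalisation falls outside 24-hour reporting and the SAE count

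*Combined protocol and SAP*

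**What the plan says.** All references are to Section 14 unless stated otherwise.

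- **Definition (Serious Adverse Events).** It opens with the words In general and continues: "a serious adverse event is defined as a harmful and undesired effect resulting from a medication or other intervention". The next sentence adds the seriousness criteria: "The event is also: life threatening/results in death OR disabling/incapacitating OR requires or prolongs hospitalization", and then "OR was otherwise unanticipated, related to the study procedures or could lead to one of the other serious event conditions".
- **Reporting to the IRBs (same subsection).** One sentence is conditional: "The PI will report to the IRBs, if mandated to do so, all serious adverse events that occur in the context of this randomized trial". The next paragraph, citing UMMS policy, is not: all adverse events and SAEs "must be reported to the institution's IRB, regardless of whether they are study related or not".
- **Recording (Adverse Events).** "All adverse events/effects will be recorded in the research record". The documentation covers a description, severity, relationship to study medication or procedures, follow-up and outcome. Seriousness is not listed as an item. Non-serious events are reviewed at a weekly study meeting.
- **Reporting to the DSMB (DSMB Reports).** Periodic reports carry data up to a cut-off, "except for Serious Adverse Events, which are to be reported within 24 hours of the event". They include a summary of all adverse events and of severe ones. The routine schedule is two meetings a year.

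**The concern.** Seriousness and causality are different questions. Seriousness concerns what happened to the participant; causality concerns why. The definition makes the second a precondition of the first, because the seriousness criteria are joined to the causal clause by the word also and do not stand as an alternative to it. The last part of the list then brings expectedness and relation to study procedures into seriousness as well.

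This matters because the label decides the route. An SAE has a 24-hour clock; a non-serious event has a weekly meeting and a periodic summary. If someone must attribute a death to a treatment before it counts as an SAE, the expedited route depends on a judgement that expedited review is meant to inform. The DSMB is asked to judge whether the nature, frequency and severity of adverse events match expectations, and it may halt the trial. Its serious-event count should not already be filtered by attribution. Section 26 foresees checking participants against local death certificates, so deaths with no attributed cause may well come to light.

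**Working it through.** The plan gives no SAE rate or count, so there is no figure to reproduce. The check is a reading of the rules, followed by two small calculations.

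**1. Apply the definition to four hypothetical events.** Limb A is the causal clause; limb B is the seriousness list.

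| Event | Limb A | Limb B | SAE as written? | SAE by outcome alone? |
|---|---|---|---|---|
| Death not attributed to any treatment | No | Yes | No | Yes |
| Admission caused by a non-study drug | Yes | Yes | Yes | Yes |
| Admission attributed to the nicotine lozenge | Yes | Yes | Yes | Yes |
| Mild but unexpected effect of the lozenge | Yes | Yes, if unanticipated suffices alone | Yes | No, unless it could lead to a serious outcome |

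The definition is too narrow in the first row. It may be too wide in the last, depending on whether the final part of the list is read as separate alternatives.

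**2. Follow the first row through the reporting rules.**
- 24-hour rule: tied to the SAE label, so it does not apply.
- Weekly meeting: applies, because the event is classed as non-serious.
- UMMS IRB: the event must still be reported as an adverse event; Section 14 gives no time limit in that sentence.
- DSMB: the event enters the summary of all adverse events in the next periodic report.

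**3. Time to the DSMB for such an event.** Inputs from Section 14: two meetings a year, report due one week before the meeting, data cut-off 14 days before the report is due. Assumption: evenly spaced meetings, so cut-offs are 52 / 2 = 26 weeks apart.
- Event to report = wait until the next cut-off (0 to 26 weeks) + 2 weeks = 2 to 28 weeks.
- Event to meeting = 1 week more = 3 to 29 weeks.

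This is what the written rules allow, not a forecast; the DSMB may choose to meet more often.

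**4. Completeness of the SAE count (illustration only).** 750 randomised, taken as 375 per arm. The event rates and attribution shares are assumptions. Counted SAEs per arm = 375 × true serious-event rate × share attributed to a medication or intervention.

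| Assumed six-month rate | Serious events per arm | Counted at 20% | Counted at 5% | Counted at 0% |
|---|---|---|---|---|
| 1% | 3.75 | 0.75 | 0.19 | 0 |
| 2% | 7.5 | 1.5 | 0.38 | 0 |
| 4% | 15 | 3.0 | 0.75 | 0 |

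At an attribution share of 20%, four in five serious events go uncounted. If the share is equal in both arms, the loss is equal too. An imbalance arises only if the share differs between arms.

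**5. The two IRB sentences.** One makes SAE reporting conditional on a mandate; the other makes reporting of all events to the UMMS IRB obligatory. They agree for UMMS only if its policy is taken to be the mandate, and the position of the PHAD IRB is then left open.

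**The case against.** The strongest reply is that little is actually lost. All adverse events are recorded, with description and outcome. Reports are reviewed by the principal investigator or a designee who is available around the clock. Serious and non-serious events alike are summarised for the IRB committees at annual review, and the DSMB receives a summary of every adverse event. The definition is introduced as a general statement, and the documents describe the foreseeable risks as small and the monitoring as matched to them.

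Most of this stands, and it limits the point. An unattributed death would not vanish from the record, and all-cause serious events could probably be reconstructed from description and outcome. But reconstruction afterwards does not restore the 24-hour notice. No seriousness item is listed, the DSMB summary speaks of severe events (severity is not seriousness), and staff are given no other definition to work from.

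Three stronger readings are tempting, and the documents do not support them.

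- **That SAE counts are biased between arms.** A reader might infer this from the simple attention control in Section 13 and from Section 11, which states staff blinding only for the initial session. But Section 13 plans no SAE comparison by arm, and the review by treatment group in Section 14 concerns outcome events under the efficacy item. Nothing says that those who attribute events know the allocation. The causal clause covers any medication in either arm, and Section 5 says the quitline already provides free nicotine replacement.
- **That the rule to report regardless of study relation has no content.** The causal clause is not confined to study treatment, so an effect of a non-study drug can be an SAE and yet be unrelated to the study. The rule also covers ordinary adverse events.
- **That unattributed events reach only the UMMS IRB.** They also appear in the DSMB summaries and in the annual summaries to the IRB committees.

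**Conclusion.** The definition is wrong as written and should be corrected. Read literally, it classes a death or hospitalisation with no attributed treatment cause as non-serious. The effect is confined to safety reporting: such an event loses the 24-hour route and may reach the DSMB 2 to 28 weeks later (assuming evenly spaced meetings), and the SAE count is incomplete by an amount the documents do not allow one to calculate. The definition also fits poorly with the rule to report regardless of study relation and with the separate relationship rating, and the two IRB sentences need reconciling.

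No primary or secondary endpoint, sample size or planned test is affected. Imbalance between arms is a possibility that depends on attribution differing by arm; it is not a finding. The conclusion rests on the literal wording; study procedures outside these documents might already apply an outcome-based definition.

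**What to change.** In Section 14:

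1. Define an SAE by outcome alone: death or a life-threatening event, disability or incapacity, hospitalisation required or prolonged, or an event that could lead to one of these. Remove from the definition the causal clause, the criterion of being unanticipated, and the criterion of relation to study procedures. Removing only the two relatedness phrases would leave unexpectedness as sufficient for seriousness.
2. Record seriousness, relationship and expectedness as separate fields beside the severity rating.
3. Apply the 24-hour rule under DSMB Reports to every SAE so defined, whatever the attribution.
4. Reconcile the conditional and unconditional sentences on IRB reporting, saying what goes to the UMMS IRB and what to the PHAD IRB.

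The cost is a wording change in one section, added fields on the adverse event form, and some additional expedited reports. Their number cannot be estimated from the documents. Mild unexpected events would drop out of the expedited route, which offsets part of the increase.
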